### 2.2 *State the hypotheses to be tested:*

The standard hypercaloric sports performance diet (500 kcal surplus energy, adequate protein and carbohydrate, judicious fat) and resistance training regimen with excess calories from peanut foods or high-carbohydrate snack foods will result in an average weight gain of 1/2 pound/week in both men and women, with the majority of that gain as lean (fat-free mass) mass.

Weight gain will be more efficient when the excess calories are from peanut foods (compared to control, high-carbohydrate foods) which will be better accepted than the control snacks.

## 3.0 Background

### 3.1 *Summarize the relevant prior research on this topic and gaps in current knowledge within the field of study:*

Many athletes and military personnel desire weight gain primarily as lean mass to improve performance and effectiveness in sport/military endeavors. While much is known about the energy restriction required to reduce body fat, little is understood about energy and macro-nutrients needed to promote healthy gains in body weight and lean mass. Typically, athletes are encouraged to increase energy intake by 400-500 kcal/day with an emphasis on adequate protein (1.2- 2.0 g protein per kg body weight for athletes), adequate carbohydrate (Butterfield, Kleiner et al. 1995, Williams, Branch et al. 2017), and judicious inclusion of healthy fat-containing, energy dense foods (e.g., peanut butter, peanuts, nuts, avocado, and dried fruit) (Grandjean 1999, Williams, Branch et al. 2017). While it is well recognized that greater gains in body mass are possible in the first year of

intense resistance training, subsequent gains taper off. Lemon, for example, estimated that body mass may increase by as much as 20% in young male body builders and football players in the first year of training, with subsequent yearly gains of only 1 to 3% (Butterfield, Kleiner et al. 1995). In general, however, gaining 1/2 to 1 lb/wk is the recommended goal (Williams, Branch et al. 2017).

Previous Studies on Weight Gain. Despite its importance, healthy weight gain is an often-ignored area of sports and human performance nutrition. Surprisingly little research has been conducted to either help establish guidelines for healthy weight gain or validate the typical aforementioned text book guidelines. In fact, initial weight gain guidelines were established using estimates of the energy required to promote muscle tissue accretion (Williams, Branch et al. 2017) from studies conducted in malnourished (Spady, Payne et al. 1976) and experimentally overfed sedentary subjects (Forbes, Brown et al. 1986). Muscle tissue itself is only~700-800 kcal/lb due to its high water content (~75% water) with only ~20% of weight as protein (Slater, Dieter et al. 2019). The additional 500 kcal/day (Butterfield, Kleiner et al. 1995, Williams, Branch et al. 2017, Slater, Dieter et al. 2019) was established based on estimates of the National Research Council that ~5 kcal are needed to support accretion of 1 gram of tissue during growth (Williams, Branch et al. 2017), which corresponds to estimates from studies of malnourished and overfed participants (Spady, Payne et al. 1976, Forbes, Brown et al. 1986).

Although methods of weight gain in athletes were heavily discussed in the mid to late 90's (Butterfield, Kleiner et al. 1995, Grandjean 1999), few studies have been conducted over the past 20 years, other than those specifically focusing on protein intake and timing on acute muscle protein synthesis (Phillips and Van Loon 2011). In one of the few studies conducted, Bartels and colleagues (Bartels, Lamb et al. 1989) found that the addition of 500 extra kcal/day during 9 weeks of heavy resistance training resulted in approximately 1/2 lb increase in lean mass/wk with no corresponding increase in body fat percentage in 12 male weight trainers. Body weight increases did not differ whether the hypercaloric diet was 45 versus 65% carbohydrate. Another semi-controlled study of Kreider et al. (Kreider, Klesges et al. 1996) examined whether supplementing the diet with one of two commercially-available weight gain powders for 28 days compared to a maltodextrin placebo influenced lean tissue accretion. Carbohydrate ingestion alone promoted a non-significant increase in lean weight of 1.47 lb (670 g) with increase in body fat weight; while ingestion of one commercial powder produced identical increases (665 g) but also an increase in body fat. The other powder promoted a significant increase of 1.56 lb (707 g) predominately as lean tissue. A more recent study by Garthe et al (Garthe, Raastad et al. 2011) examined the effect of nutritional counselling (designed to create a 500 kcal/day surplus) compared to ad libitum dietary intake on changes in body composition during an 8-12 week focused resistance training period in 21 elite Norwegian athletes (including 4 women). Individually-prescribed hypercaloric meal plans and counseling resulted in successful short and long-term gains in total body and lean mass. To our knowledge, no studies have evaluated intentional weight gain in active women (who may also desire weight gain (Minnick, Raffoul et al. 2020)) or focused on the health implications of such gain in athletes.

Benefit of Peanuts and Peanut Products in Healthy Weight Gain. Research and observations by sports dietitians suggest that active individuals interested in weight gain

often rely on commercially-available powders (Kreider, Klesges et al. 1996), energy bars and other high-protein specialized products as a source of additional calories (Minnick, Raffoul et al. 2020) during weight gain attempts. These food items, however, are considered ultra-processed foods (Pagliai, Dinu et al. 2021). A growing body of evidence links ultra-processed food consumption to adverse health outcomes, including increased risk of cardio-metabolic disease, stroke and depression (Pagliai, Dinu et al. 2021). Given the increased interest in the health benefits of whole-food and plant-based diets (and the combination of the two), peanuts are an ideal source of high-quality plant-based protein for consumers interested in weight/lean mass gain. Peanut butter, peanuts, and nuts are typically suggested foods to include in healthy weight gaining meal plans (Grandjean 1999) because they are both nutrient- and energy-dense. Peanuts contain nutritionally significant quantities of potassium, magnesium, copper, iron, and fiber (Kholief 1987). Peanut protein provides substantial quantities of most amino acids, but it is low in methionine and tryptophan, and particularly high in arginine relative to other proteins. Additional methionine and tryptophan are easily obtained by combining peanuts with oats, rice, wheat and nuts. The high arginine content along with high concentrations of phytonutrients may offer health benefits and reduce risk of chronic and inflammatory diseases. Arginine in particular is a precursor to the potent vasodilator, nitric oxide. External nitric oxide has the potential to lower blood pressure and promote exercise efficiency (Jones, Vanhatalo et al. 2021). Additionally, peanuts and peanut butter are affordable, readily available, and add flavor and versatility to the diet, making peanuts an ideal food to incorporate into a healthy weight gain meal plan.

*3.2 Describe any relevant preliminary data:*

[name] has previously completed a similar diet-induced weight gain protocol in non-athletes; This protocol overfed 14 male (Gentile, Orr et al. 2007) and 3 female (unpublished data) participants ~1000 calories per day over baseline requirements using commercially-available food/beverages as the source of excess daily energy.

*3.3 Based on the existing literature, provide the scientific or scholarly rationale for and significance of your research and how will it add to existing knowledge:*

With increased prevalence of overweight and obesity in the U.S and worldwide, emphasis on understanding healthy weight gain in both the general population and among athletes and military personnel has been largely ignored. However, a recent survey of close to 977,000 Canadian adults, aged 17-32 years, found that ~23% of men and 6% of women reported attempting to gain weight in the past 12 months (Minnick, Raffoul et al. 2020). In athletes (Garthe and Maughan 2018) and military personnel (Bukhari, DiChiara et al. 2021), desire to gain weight is a top reason reported for supplement use. Attempts to gain weight included eating more overall and eating more protein (Minnick, Raffoul et al. 2020) through consumption of foods that are often ultra-processed, and likely to

have negative health effects. Previous studies by [name] group found that weight gain of 5 kg using such foods increased systolic and diastolic blood pressure even in those who were relatively fit (Gentile, Orr et al. 2007). The proposed study would serve as an important first step in helping understand the gaps in knowledge related to healthy weight gain. Findings would be of interest to sports and military dietitians and would be expected to lead to better understanding of the energy surplus needed to overcome metabolic adaptation and develop more targeted weight prescriptions. Results would inform the design of more effective weight gain meal plans, not only in athletes and military personnel, but also in older individuals and in clinical populations where promotion of weight gain is advocated. Future trials based on findings of the proposed study will likely explore benefits of peanut products in healthy weight in a variety of populations

## 4.0 Study Endpoints

4.1 *Describe the primary and secondary **study** endpoints. See links below for discussion of study endpoints and how they may differ from study objectives. These are most common in clinical trials but are sometimes applicable to other types of biomedical research, as well as social, behavioral, or educational research. See link below for a discussion.*

[https://docs.google.com/document/d/1Wocz7K7a0hCQJPPO\\_khh511SQQjhGDDGHzcOPRHR5Tw/edit?usp=sharing](https://docs.google.com/document/d/1Wocz7K7a0hCQJPPO_khh511SQQjhGDDGHzcOPRHR5Tw/edit?usp=sharing)

### Secondary Endpoints

- Change in Resting Metabolic Rate/Resting Energy Expenditure
- Change in Hormone and Metabolic Markers in Blood including testosterone (free & total), growth hormone, insulin-like growth factor, leptin, insulin, thyroid hormones, cortisol and ghrelin and urinary creatinine and urinary iodine
- Change in Strength (all muscle groups)
- Change in Aerobic Fitness
- Change in Walking Economy

Change in and absolute values of Health Outcomes (blood pressure, serum cholesterol, fasting and 24-hour glucose concentration, and hydration status)

Change in Dietary Patterns

Change in Physical Activity and Structured Exercise

Change in Appetite

Baseline vitamin D intake and status and change in serum vitamin D

**4.2** *Describe any primary or secondary safety endpoints. These should be included for all studies that are greater than minimal risk. (Minimal risk: The probability and magnitude of harm or discomfort anticipated in the research that are not greater in and of themselves than those ordinarily encountered in daily life or during the performance of routine physical or psychological examinations or tests.):*

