## 1.0 Study Summary

Study Title	Exploring the Role of Peanuts in Enhancing Healthy Weight Gain in Athletic Individuals
Study Design	Randomly Assigned Intervention Study
Primary Objective	Determine the efficacy of the standard hypercaloric sports performance diet (500 kcal surplus energy, adequate protein and carbohydrate, judicious fat) and weight training regimen with excess calories from peanut foods or high-carbohydrate snack foods on weight and lean mass gains over 10 weeks in athletic men and women desiring weight gain.
Secondary Objective(s)	Secondary Aim: Evaluate the ease and acceptability of whole peanuts, peanut butter and peanut-based healthy snacks relative to high-carbohydrate snacks as part of the standard hypercaloric regimen. Exploratory Aim: Examine the effect of potential adaptive factors (increased resting metabolism, decreased appetite) and individual characteristics (sex, age, training history, somatotype) on weight and lean mass gains.
Study Population	Athletic and military men and women who desire weight gain primarily as lean mass to improve performance and/or effectiveness in sport/military endeavors.
Sample Size	32 (16 men and 16 women)
Research Intervention(s)/ Investigational Agent(s)	Men and women will be randomly assigned to a peanut intervention or control group (8 men and 8 women per group); Each group will undergo a 10-wk diet and weight training regimen designed to promote healthy weight gain.
Study Duration for Individual Participants	12 to 13 weeks including screening, baseline testing, the 10-week intervention and post-testing
Acronyms and Definitions	DXA, Dual-Energy X-ray Absorptiometry; TSH, thyroid-stimulating hormone; CBC, complete blood count; RMR, resting metabolic rate; REE, resting energy expenditure; VO 2 max, maximal oxygen uptake during exercise, also known as aerobic capacity; Reps; repetitions; CGM, continuous glucose monitoring; ISAK, International Standards for Anthropometric Assessment; ACSM, American College of Sports Medicine; IUSCA, International Universities Strength and Conditioning Association; HIP Laboratory, Human Integrated Physiology Laboratory; NEM Laboratory, Nutrition and Exercise Metabolism Laboratory

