## 5.0 Study Design and Statistical Analysis Plan

**5.1** *Describe the basic study design/approach (e.g., qualitative study using five focus groups of first year students to describe assimilation into the university community; randomized controlled trial of a behavioral change intervention to increase dietary intake of whole grains; pre- post-test evaluation of new pedagogical techniques to improve adult literacy):*

This study is a randomly assigned intervention study that will evaluate the effect of a 10-wk diet and exercise regimen designed to promote healthy weight gain in athletes and military personnel (who desire weight gain). This will include increasing energy intake by 500 additional kcal/day (above weight maintenance diet) through daily provision of either peanut-based whole foods/snacks (peanut group) or a similar, high-carbohydrate, peanut-free snack (control group) along with a supervised resistance training regimen.

*5.2 Describe corresponding data analysis plan/approach (e.g., content analysis of focus group transcripts; descriptive analysis followed by linear regression modeling; nonparametric analysis of pre- and post-test measures):*

Data will be analyzed using IBM SPSS statistics software. Repeated measures ANOVA will be used to assess changes in dependent variables including participant body weight, body composition and anthropometric variables by group and across time (Aim 1). Student t-tests and simple and partial correlation statistics (Pearson Product or Spearman Rank) will be used to evaluate the magnitude of change in body weight/lean mass according to participant characteristics (sex, age, training status, somatotype) and significant adaptive changes in thermogenesis and appetite (Aim 3). Descriptive statistic methodologies will be applied to evaluate the ease and acceptability of peanut foods in the weight gain meal plan (Aim 2). The significance level will be set a priori at  $p < 0.05$

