## 8.0 Procedures Involved

### 8.1 Describe and explain the study design:

Sixteen men and sixteen women between the ages of 18 and 40 will be randomly assigned to the peanut intervention or control group (8 men/8 women/group). A computer program with a random number generator will be used by the study coordinator to assign male participants and female participants to the peanut or control group (i.e., each sex will be separately randomized).

As outlined in the table, eligible participants will undergo a 10-wk diet and training regimen designed to promote healthy weight gain. This will include increasing energy intake by 500 additional kcal/day (above their typical weight maintenance diet and accounting for energy requirements of resistance training) through provision of peanut-based whole foods/snacks or high-carbohydrate containing control snacks along

with a supervised rigorous resistance training regimen designed to promote muscle hypertrophy. After providing informed consent, participants will be randomly assigned to the peanut or control group based on sex. Outcome data will include assessment of body mass, total and regional body composition via DXA and body anthropometrics, skinfolds and somatotyping using the International Standards for Anthropometric Assessment (ISAK) (Stewart, Marfell-Jones et al. 2011) along with measures of resting metabolic rate (RMR), circulating hormones and serum/plasma biomarkers. The latter includes measurement of potentially important hormones/ biomarkers of anabolism, stress, overfeeding, and cardiometabolic health. Compliance to the nutrition and exercise regimen will be evaluated at regular intervals and include collection of 3-day food records (performed at baseline and 3-days prior to each assessment point) and physical activity data collected by digital technology (Garmin Vena SQ smart watch and My PT Hub app).

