**Resistance Training.** Participants will undergo rigorous resistance training three days/week in the NEM laboratory under close supervision. The following will be performed with weight machines (Nautilus) and free weights: leg press, squat, leg extension, leg flexion, toe raise, lat-pull down, dead lift, shoulder press, bench press, bicep curl, triceps extension and abdominal twist/crunch. The overall goal will be to have participants perform 10 sets of exercises that work the major muscle groups each week in accordance with a recently published position stand of the International Universities Strength and Conditioning Association (IUSCA) (Schoenfeld et al 2021) with slightly different set of exercises performed on each of the three days. Participants will begin with light to moderate resistance for 8-15 repetitions, after which resistance will be gradually increased in the next 5 workouts. After that, three to five sets of each exercise will be completed using modified methodology of Bartels et al (Kreider, Klesges et al. 1996) (previously shown to effectively promote weight gain) in accordance with the latest

guidelines for promoting muscle hypertrophy (Schoenfeld et al 2021). . Resistance will be adjusted upward after 8 repetitions are fully executed using proper technique. Participants engaged in a sport or military training activity will be instructed to maintain their normal training throughout the study.

Table 1. Overview of Data Collection

Overview of Data Collection	Baseline	3 wk	7 wk	11 wk
Body Mass (weight)	x	x	x	x
Body Composition by DXA and spot urine sample; Pregnancy test by urine in female participants	x	x	x	x
Skinfolds & circumferences	x			x
Resting metabolic rate-RMR	x	x		x
Blood via venipuncture and Urine vis 24-hr collection				
CBC and TSH	x			
Testosterone (free &total)	x	x	x	x
Growth Hormone	x	x	x	x
Insulin-like growth factor	x	x	x	x
Leptin	x	x	x	x
Insulin	x	x	x	x
Free T4	x	x	x	x
Cortisol	x			x
Ghrelin	x	x	x	x
Urinary creatinine and urinary iodine	x			x
Health outcomes				
Blood Pressure	x	x	x	x
Serum Lipids	x			x
Serum Vitamin D	x			x
Fasting blood glucose	x			x
Continuous glucose monitoring	x			x
Compliance and Fitness Testing				

Strength Testing	x			x
Aerobic Capacity (VO2max) and walking efficiency	x			x
Food Records and Appetite rating for 3-day	x	x	x	x
Vitamin D Food Frequency and Lifestyle Questionnaire	x			
Exercise tracking for 3-days (smart watch)	x	x	x	x
Daily snack tracking logs and exercise logs	↔	↔	↔	→

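### Section 5.2 gives no scale, baseline covariate or sex term for hormones; if its ANOVA is applied to testosterone on the raw scale, men dominate the result and power may be lost

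*Combined protocol and SAP*

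**What the plan says.** Section 4.1 makes hormone change a secondary endpoint: "Change in Hormone and Metabolic Markers in Blood including testosterone (free & total), growth hormone, insulin-like growth factor, leptin, insulin", followed by further markers. It does not say whether change is absolute, relative or on a log scale. Table 1 in section 8.1 schedules free and total testosterone at baseline and at weeks 3, 7 and 11.

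Section 5.2 gives the between-group method: "Repeated measures ANOVA will be used to assess changes in dependent variables including participant body weight, body composition and anthropometric variables by group" and over time. This is tied to Aim 1. The examples are body measures, and hormones are not among them, but the list is open. Section 5.2 mentions no transformation, no baseline covariate and no sex factor. Sex appears there only under Aim 3, where t-tests and correlations "will be used to evaluate the magnitude of change in body weight/lean mass according to participant characteristics (sex, age, training status, somatotype" and so on.

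Section 8.1 says that "each sex will be separately randomized", and section 1.0 plans 8 men and 8 women per group. Section 14.1 bases the sample size on feasibility and budget and allows recruitment of up to 40. No power, effect size or SD is given for any endpoint.

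**The concern.** An analyst who looks in section 5.2 for a way to compare hormone change between groups finds only this ANOVA. For most body measures the scale matters little. Testosterone differs if men's levels are several times women's and changes are roughly proportional to level. In raw units a given percentage change is then many times larger in a man than in a woman. A mean over both sexes follows the men, and so does the error variance. The women add half the participants but little information.

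Two things are at stake. A real effect on testosterone could be missed, in a trial whose size leaves no known margin. A pooled result could also be reported for both sexes while resting almost wholly on 8 men against 8 men. Section 3.1 gives the lack of studies of intentional weight gain in active women as a gap in knowledge, so the second matters.

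**Working it through.** There is no figure in the plan to reproduce, because no power is stated. The check is conditional.

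**From the documents:** 8 men and 8 women per arm (section 1.0); significance level 0.05 (section 5.2), taken as two-sided because sidedness is not stated; randomization separate by sex (section 8.1).

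**Assumed, because the documents give no values:** male/female ratio of level R, mainly 5 to 20; the same proportional effect and the same relative error in both sexes, varied in step 3.

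**Step 1: who carries the raw-scale result.** With equal numbers of each sex,
- men's weight in the estimated effect = R/(1+R);
- men's share of the error variance = R²/(1+R²);
- efficiency relative to the log scale = (1+R)²/[2(1+R²)], which multiplied by 16 gives the effective number per arm.

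| R | Men's weight | Men's share of variance | Efficiency | Effective n per arm |
|---|---|---|---|---|
| 2 | 2/3 = 67% | 4/5 = 80% | 9/10 = 0.900 | 14.4 |
| 5 | 5/6 = 83% | 25/26 = 96.2% | 36/52 = 0.692 | 11.1 |
| 10 | 10/11 = 91% | 100/101 = 99.0% | 121/202 = 0.599 | 9.6 |
| 20 | 20/21 = 95% | 400/401 = 99.8% | 441/802 = 0.550 | 8.8 |

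Set the log-scale analysis at 80% power (standardized effect 1.025, 16 per arm). The noncentral t then gives, on the raw scale, 76% at R = 2, 65% at R = 5, 58% at R = 10 and 55% at R = 20. With 20 per arm and the effect reset to 80% power, these values move by no more than 0.1 point. The formula is optimistic for the raw scale. It ignores the spread of baseline levels within each sex and the difference in mean change between the sexes, both of which add raw-scale error.

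**Step 2: simulation with those sources included.** Settings: 5,000 trials per row, within-person CV 20%, between-person CV 30%, a 30% rise in both sexes, and one baseline-to-follow-up change per participant.

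| R | Raw, pooled | Raw + sex | Log change + sex | Log ANCOVA + sex | Raw, men only (8 v 8) |
|---|---|---|---|---|---|
| 1 | 73% | 73% | 73% | 79% | 43% |
| 5 | 53% | 56% | 73% | 78% | 41% |
| 10 | 47% | 51% | 73% | 78% | 43% |
| 20 | 42% | 46% | 73% | 78% | 43% |

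Repeat runs agree to within about 3 points (at R = 20, pooled raw power came out between 40% and 43%). At R = 20 the pooled analysis does no better than the men alone. A sex term on the raw scale recovers only 3 to 4 points at R = 5 to 20. For a 20% rise, the raw scale gives 22-30% and log change with sex about 43%.

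Sex is also needed in the log model. Log ANCOVA without it has 73-74% power against 78% with it, because across the sexes log baseline mostly reflects sex.

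**Step 3: vary the assumption that favours the log scale (R = 5 to 20).**

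| Case | Raw | Log |
|---|---|---|
| 30% rise in men only | 41% (with sex) | 23-24% (log change + sex) |
| 30% rise in women only | 4-7% (pooled) | 24-27% (log ANCOVA + sex) |
| Rise in both, women's within-person CV 40% | 46-50% (with sex) | 38% (log change + sex) |
| Same case | 41-50% (pooled) | 47-50% (log ANCOVA + sex) |

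**Step 4: type I error.** With no effect, rejection rates across the models compared were about 4-6%.

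**The case against.** The strongest objection is that section 5.2 never mentions hormones. A reader might infer that the plan commits to pooling men and women in raw units. It does not: it is silent, and an analyst could take logs or report by sex without contradicting it. That stands, so the point is an unspecified analysis with a poor default.

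Second, the size of the loss rests on figures that the documents do not contain, and the assumption of equal relative effects favours the log scale. This stands in part. If only men respond, raw units do better. If women's relative error is twice men's, a log change score does worse than the raw scale, but with both baseline and sex in the log model the disadvantage largely goes. The men-only case also has a mirror image: an effect confined to women is close to invisible in raw units.

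Third, a reader might infer that every listed hormone needs a log scale. The calculations do not support that. At ratios of 1 to 2 the formula loss is only 0 to 4 points.

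Fourth, a reader might infer that the test would be invalid because variances differ between the sexes. It would not: randomization by sex keeps the arms comparable, and type I error stays near 5%.

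Last, this is a secondary endpoint. Section 2.2 has no hormone hypothesis, and the adaptive factors named in Aim 3 are resting metabolism and appetite. That limits the consequence.

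**Conclusion.** The point holds in conditional form and is minor. Section 5.2 leaves scale, baseline and sex unspecified for hormones, and drops the factor by which participants are randomized. If testosterone goes through its ANOVA in raw units, men carry 83-95% of the estimated effect at ratios of 5 to 20. Power for a 30% rise in both sexes is then about 43-53%, against about 78% for log ANCOVA with sex, a gap of roughly 25 to 35 points.

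This rests on the assumed ratio and CVs, on a common relative effect, and on a single change per participant. A four-visit ANOVA would have different absolute power, but the men's dominance of the raw scale would remain. The gap is small or absent if women's relative error is about twice men's, and reverses if only men respond. The harm is to power and to what a pooled result can be said to describe. The comparison between arms is not biased, and no figure in the plan is wrong.

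**What to change.** In section 5.2, state that free and total testosterone will be analysed on the log scale with log baseline and sex (the randomization stratum) in the model. Report the peanut/control ratio of geometric means with its 95% CI, and give results by sex descriptively. State a rule for values below the assay's detection limit.

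For the other hormones, include baseline and sex as covariates and state the scale for each.

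The cost is a few sentences in the plan and slightly more analysis work. Effects on testosterone will be ratios, not differences in absolute units. No extra participants, visits or samples are needed.
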